Seizure Frequency through Diary Data Collection			X	X	X	X
NIH Emotional Measures or Bayley Emotional Scales ^d			X			
Social Determinants of Health data collection			X			
Titrate CBD (if needed)					X	X
Dispense Medication			X		X	X
AE/SAE Monitoring/Reporting				X	X	X

UAB CBD Program: Children's Protocol Schedule of Events (Patients 1 years to 18 years of age) -Page 3 of 5

Activities/Procedures:	SV7/Day 84 (+/- 3 days) or Follow up study visit 28 days after after Target dose is reached:	SV10/Day168/Wk 24/Month 6 (+/- 7 days), SV 14/Day 504/Wk 96/Month 24 (+/- 7 days), SV18/Day 840/Wk 192/Month 48 (+/- 7 days):	SV8/Day 112/Wk 16/Month 4 (+/- 7 days), SV9/Day140/Wk 20/Month 5 (+/- 7 days), SV11/Day 252/Wk 36/ Month 9 (+/- 7 days), SV12/Day 336/Wk 48/ Month 12, SV13/Day420/Wk72/ Month 18, SV15/Day 588/Wk 120/ Month30, SV16/Day 672/Wk 144/Month 36, SV17/Day 756/Wk 168/ Month 42:	Unscheduled Visit or Early Termination Visit (prior to year 1 visit):	Post-Termination Study Visit (approximately 28 days after CBD wean):
Seizure Frequency through Diary Data Collection	X	X	X	X	X
Chalfont Seizure Severity Scale	X	X	X	X	X
Neurological Exam	X	X	X	X	X
General Physical Exam	X	X	X		
Laboratory Assessments ^e	X ^e	X ^e	X ^e	X ^e	X ^e
Electrocardiogram (ECG)				X (at early term visit prior to year 1 only)	X
Urine Pregnancy Test (only for women of child bearing potential)	X	X	X	X	X
Menstrual History Data	X	X	X	X	X
EEG ^a (30-60 minute) duration	X	X ^a	X ^{a,g}	X ^c	
Vital Signs (age, weight, height, HR, BP,	X	X	X	X	X
Pediatric Cognitive Testing (NIH Toolbox), ABAS-II or Bayley Functional Scales ^b		X		X ^c	
Quality of Life in Childhood Epilepsy (QOLCE)		X		X ^c	
Adverse Events Profile	X	X	X	X	X
Columbia Suicide Severity Rating Scale (C-SSRS)	X ^a	X	X	X	X
Child Behavioral Checklist Assessment	X	X			
NIH Emotional Measures or Bayley Emotional		X (SV10 only)	X (SV12 only)		
Social Determinants of Health data collection		X		X ^c	
Titrate CBD (if needed)	X	X	X	X	
Dispense Medication	X	X	X	X (if needed)	
AE/SAE Monitoring/Reporting	X	X	X	X	X

X* =Participants' who have an Enrollment Visit and Study Visit1/Day 0 conducted on the same day will have the following activities performed only once during the visit: Urine Pregnancy test, Seizure Frequency Calendar, Chalfont Seizure Severity Scale, Neurological Exam, General Physical Exam, and Vital signs.

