^aAn EEG will be performed at the first of the follow up study visit where the Principal Investigator determines the patient has reached their target dose of CBD. At the discretion of the investigator, an additional EEG may be performed at follow up visits, depending on clinical course.

^bNIH Toolbox Measures include: For ages 3-6 years: Dimensional Change Card Sort Test (DCCS), Flanker Inhibitory Control and Attention Test, Picture Sequence Memory Test, Picture Vocabulary, Oral Reading Recognition test (for children who have developed letter and/or word recognition skills). For ages 7-14 years: Dimensional Change Card Sort Test (DCCS), Flanker Inhibitory Control and Attention Test, Picture Sequence Memory Test, Picture Vocabulary Test, Oral Reading Recognition Test, List Sorting Working Memory Test, Pattern Comparison Processing Speed Test. For ages 15-18 years: Dimensional Change Card Sort Test (DCCS), Flanker Inhibitory Control and Attention Test, Picture Sequence Memory Test, List Sorting Working Memory Test, Pattern Comparison Processing Speed Test, Reading Recognition Test. For participants between the ages of 1 year (12 months) and less than 3 years of age, and/or who are unable, due to cognitive impairment, to complete the Cognitive subtests from the NIH Toolbox, their legal guardian will be asked to complete the Adaptive Behavior Assessment Scale – II (ABAS-II). The ABAS-II measures adaptive behavior, using parent-report to evaluate function across a variety of environments. Test results include four domain composite scores (Conceptual, Social, Practical, and General Adaptive Composite) and 10 skill area scores (Communication, Community Use, Functional Academics, Health and Safety, Home or School Living, Leisure, Self-Care, Self-Direction, Social, and Work/Motor). For participants < 3 years of age, Bayley Scales of Infant and Toddler Development®, Third Edition (Bayley-III®)-Functional Assessments will be completed by the parent or LAR of the participant, instead of the NIH Cognitive assessments.

^cDuring any early termination or unscheduled visit, individual decision will be made by the managing study doctor regarding further participation, medication titration (up or down), medication wean, etc. If the patient and provider agree on terminating participation prior to 1 year visit, the following data points will be collected at that visit (or at year 1 visit).

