 - o NIH TB SR Perceived Hostility SF
 - o NIH TB SR Perceived Rejection SF
- Stress & Self Efficacy
 - o NIH TB SSE Perceived Stress CAT
 - o NIH TB SSE Self-Efficacy CAT

For participants < 3 years of age, Bayley Scales of Infant and Toddler Development®, Third Edition (Bayley-III®)-Emotional Assessments will be completed by the parent or LAR of the participant, instead of the NIH Emotional Measures assessments.

- Conditional Procedure: EEG— a video EEG (30-60 minutes recording) will only be performed at the first follow up study visit where the participant reaches their target dose of CBD, as judged by the clinician. At the discretion of the investigator, an additional EEG may be performed at follow up visits, depending on clinical course.
- Study Drug CBD Medication Order and/or adjustments in CBD dosing (as described under Dosing Adjustment/Schedule section above)

Unscheduled Study Visit:

Unscheduled study visit(s) will be performed when deemed necessary by the study physician. Indication for such visit will include e.g., side effects, increase in seizures, request to discontinue CBD treatment, etc.

Procedures for these visits will include:

- Adverse Event and Serious Adverse Event Monitoring (e.g., increase in seizure frequency by more than 100% leading to emergency room visit or hospitalization)

- Seizure Diary Data reviewed and collected by study staff
 - Menstrual History collected by study staff
 - Chalfont Seizure Severity Scale
 - Vital signs: Age, Weight, Height, Heart Rate, and Blood Pressure, Temperature
 - Urine Pregnancy Test (only for women of child bearing potential)
 - Neurological Examination
 - Columbia-Suicide Severity Rating Scale (C-SSRS) Questionnaire
 - CBC and CMP (Study doctor may order additional laboratory testing (blood and/or urine tests) to assess for side effects and toxicity. The laboratory assessments would include: Liver Functional Tests (LFTs), Urinary Analysis and any anti-epileptic drug (AED) levels), AEP
 - Study Drug CBD Medication Order and/or adjustments in CBD dosing (if needed)
- Individualized decision will be made by the managing study physician regarding further participation, AED medication titration (up or down), CBD medication adjustment/wean, etc. If the patient and provider agree on terminating participation prior to 1 year visit, the following data points will be collected at that early termination visit:
- Video EEG (30-60 minute recording)
 - ECG

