AEs that occur following completion of study termination/early termination procedures should be recorded on the AE page of the source documents only if the investigator considers the event as clinically significant and as related to study medication or study procedures.

All adverse events that are deemed to be serious and meet the definitions provided in section below for serious adverse events will be reported as SAEs.

Serious Adverse Events :

Serious adverse event is defined as “ANY TREATMENT EMERGENT SAE THAT OCCURS AFTER THE SIGNING OF THE INFORMED CONSENT FORM through 30 DAYS after administration of the last dose of study medication. Any AE that results in any of the following outcomes will be considered an SAE. The following outcomes are defined according to Code of Federal Regulations (CFR) Title 21 part 312.32.

- Death
- Life-threatening situation (subject was at risk of death at the time of the event. This does not refer to an event that might have caused death if it was of greater intensity.)
- Inpatient hospitalization or prolongation of existing hospitalization
- Persistent or significant disability or incapacity
- Congenital anomaly or birth defect
- Important medical events that may not result in death, be life-threatening, or require hospitalization but may jeopardize the subject and may require medical or surgical intervention to prevent one of the above outcomes (based upon appropriate medical judgment), e.g., allergic bronchospasm requiring intensive treatment in an emergency room or at home, blood dyscrasias or convulsions that do not result in inpatient hospitalization, or the development of drug dependency or drug abuse.

The term “severe” is often used to describe the intensity (severity) of a specific event (as in mild, moderate, or severe pain); the event itself, however, may be of relatively minor medical significance (such as severe headache). By contrast, the term “serious” is used to describe an event based on an event outcome or actions usually associated with events that pose a threat to a patient’s life or functioning. Seriousness (not severity) serves as a guide for defining regulatory reporting obligations.

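### Restricted AE recording starts at completion of termination procedures rather than at the last dose, so some non-serious AEs during a CBD wean may go unrecorded

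*Protocol*

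**What the plan says.** The rule closes the Adverse Events part of the protocol's Safety Data section: "AEs that occur following completion of study termination/early termination procedures should be recorded on the AE page of the source documents only if" a two-part test is met, namely that "the investigator considers the event as clinically significant and as related to study medication or study procedures". Both conditions must hold. The protocol does not define which procedures these are or when they are complete.

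Earlier in the same section the rules are wider. All treatment-emergent AEs go on source documents, and AEs that start or worsen after consent go on the AE form. Neither rule has an end date.

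The Serious Adverse Events section uses a different clock: SAEs are collected from consent until 30 days after the last dose.

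On stopping the drug, Dosing Adjustment/Schedule rules out abrupt withdrawal. It sets a default taper of 5 mg/kg/day every two weeks, which the provider may vary. Footnote c to the Schedule of Events lists, among the decisions taken at an early-termination or unscheduled visit, "further participation, medication titration (up or down), medication wean, etc". The Unscheduled Study Visit section likewise includes "CBD medication adjustment/wean". The last column of the schedule is headed "Post-Termination Study Visit (approximately 28 days after CBD wean"), and the row "AE/SAE Monitoring/Reporting" is marked there.

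**The concern.** Safety is the primary outcome of a single-arm study, so the period of full AE recording should match the period on drug. If a child completes the early-termination visit and then weans over several weeks, the child is still taking CBD while the narrower rule applies. A non-serious event could then be left out because the investigator thought it unrelated, even if it was clinically significant, or because it was thought insignificant. The protocol ties SAE collection to the last dose but ties ordinary AE recording to a visit procedure. At stake is the completeness of the AE tables for children who leave, a group in which tolerability problems may be more frequent.

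**Working it through.** The plan states no figure on this point, so the check compares the text and then works out the length of the wean.

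**1. Can the wean follow the early-termination visit?** Yes.
- The section on withdrawal and discontinuation holds that visit when the subject wishes to stop the drug, which implies the child may still be taking it.
- Footnote c and the Unscheduled Study Visit section list the wean among decisions made at such a visit.
- The schedule marks titration and, if needed, dispensing in the column shared by unscheduled and early-termination visits.
- The next column is a separate visit timed from the wean.
- Abrupt stopping is ruled out.

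**2. Can the wean come first?** Also yes.
- Dosing Adjustment/Schedule allows tapering at ordinary biweekly visits, where full AE recording applies.
- The text section on the post-termination visit dates it about 28 days after the end of the study, whereas the schedule dates it about 28 days after the wean. Read together, these could mean that the wean ends before the study does.

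**3. Length of a wean that follows the visit.** Inputs from Dosing Adjustment/Schedule: steps of 5 mg/kg/day, 14 days apart; standard maximum 25 and absolute maximum 50 mg/kg/day. Input from the schedule: post-termination visit about 28 days after the wean. Assumption: the first cut is made at the termination visit.

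Wean days = (D/5 − 1) × 14. Days to the post-termination visit = wean days + 28.

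| Exit dose D (mg/kg/day) | Wean (days) | Termination visit to post-termination visit (days) |
|---|---|---|
| 5 | 0 | 28 |
| 10 | 14 | 42 |
| 15 | 28 | 56 |
| 20 | 42 | 70 |
| 25 | 56 | 84 |
| 50 | 126 | 154 |

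If the first cut comes two weeks after the visit, add 14 days: from 25 mg/kg/day the figures are 70 and 98. A different rate chosen by the provider changes all of them.

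**4. Which summaries are affected, and in which direction?** Take the summaries named in the protocol's Data Analysis section and in the SAP, and suppose some wean AEs are omitted.
- *Percent of children with an event:* the denominator is unchanged, so the figure falls or stays the same. This table covers safety-outcome events and others reported as meaningful, so the main loss is non-serious events judged significant but unrelated.
- *Number of events:* falls or stays the same. It is worded more widely, so insignificant events can drop out too.
- *Mean number of events among affected children:* either direction. For illustration, two children with 3 and 1 events average (3 + 1)/2 = 2.0. Omit the second child's only event and the mean is 3/1 = 3.0. Omit one of the first child's events instead and it is (2 + 1)/2 = 1.5.
- *Rate per unit of exposure:* neither document says whether wean time counts. If it counts, omitting events lowers the rate. If wean time is left out as well, (E1 + E2)/(T1 + T2) becomes E1/T1 (E events and T time; 1 before the wean, 2 during it). That is lower or higher according to whether E2/T2 exceeds E1/T1.

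The SAP analyses the first 12 months, so only wean time within that period reaches its tables.

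**The case against.** The best defence is that the gap depends on an order of events the protocol does not require. If the wean is done at ordinary visits, or if the post-termination visit is itself a termination procedure, full recording continues throughout. The general all-AE rules also have no end date. This stands in part: the finding is a conflict between rules, and a reader who infers that wean AEs are certainly lost goes beyond the text. But neither closing reading is stated, and the restrictive sentence is the more specific rule. The protocol lists early-termination data points separately from the post-termination visit. The Data Safety Monitoring Board section also provides only an early-termination visit if the study is stopped, so a post-termination visit may not always exist to defer the restriction.

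A second defence is that the serious hazards are already covered. This largely stands. The SAE window runs past the wean, and the SAE examples include convulsions without admission and blood dyscrasias. The wean hazard the protocol names, worsening seizures, is therefore mostly captured.

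Third, a reader might infer that the primary blood pressure, heart rate and laboratory items are lost because those outcomes require significance but not relatedness. The documents do not support that. The restriction concerns the AE page, while vital signs, CBC and CMP are scheduled at the post-termination visit and collected regardless.

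Last, the intervals in the table are times to the next scheduled check, not unobserved time. Families can report at any time and unscheduled visits are available. However, these routes detect events; they do not exempt them from the recording restriction.

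**Conclusion.** The concern holds as a minor inconsistency. Full AE recording ends on a trigger that, on one permitted reading, can precede the last dose by 8 weeks from the standard maximum dose, or by 18 weeks from 50 mg/kg/day. Both figures assume the default rate and a first cut at the termination visit. The 50 mg/kg/day case should be uncommon, since doses above 25 are reserved for children with clear improvement and few side effects.

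What is exposed is non-serious AEs judged insignificant or unrelated, in children whose wean follows the termination visit. A reader might infer that the rule can only lower the reported AE figures. That is true of the percent of children affected and of the event count, but not of the mean per affected child, and it is unsettled for the exposure-based rate. The documents give no number of such children, no exit doses and no AE rates during weaning, so the effect on the tables cannot be computed.

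**What to change.** Two wording changes to the protocol:

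1. In Adverse Events, start the restricted recording only after the post-termination visit, or 28 days after the last CBD dose if that visit is missed. State that all AEs are recorded in full through the wean.
2. In the Post-Termination Study Visit section, date the visit from the end of the CBD wean, as the Schedule of Events already does.

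The cost is slightly more AE data entry for children who leave and possibly slightly higher reported AE counts. No visit or procedure is added.

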If the adverse event meets the criteria of an SAE, it should be reported as soon as possible, within 24 hours of the event. The study personnel should enter this information into the UAB study database. Each study investigator should also report these related SAEs to one of the co-directors of the UAB CBD program, UAB IRB, and GW Pharmaceuticals.

Any severe and unexpected SAE's will be reported to the Food and Drug Administration agency.

Data Safety Monitoring Board (DSMB):

Study **Data Safety Monitoring Board (DSMB)** will be established:

A Data Safety Monitoring Board has been established for monitoring to detect risks and monitor safety. The DSMB will meet after enrolling the first 12 subjects but not later than 6 months after the initiation of the study (whichever comes first). DSMB will then meet every 6 months until the last visit has been completed. Last DSMB meeting will be after the last subject exits the study and final statistical analyses are available. Meetings will be either in person or via e-mail as determined by the DSMB Chair. While DSMB will periodically review all study data, incidence of severe adverse events will be monitored for the purpose of study participation continuation/discontinuation. If more than 25% of participating subjects have severe adverse events (SAEs), deemed to be drug related, indicating an unfavorable benefit-to-risk profile, the study will be terminated.

Once the study staff receives documentation of an SAE, including death and regardless of causality, the information will be forwarded to the Principle Investigator, DSMB Chairperson, and the Program Manager. These persons will assure that the documented SAE information is sent, within 24 hours of receipt, electronically and securely to the other DSMB members for review.

At each DSMB meeting, the board will evaluate whether there are significant issues pertaining to study design, conduct, or safety results that warrant a recommendation to the principal investigator. The DSMB may make a recommendation regarding any aspect of the conduct or design of the study, including early termination. After each planned meeting, the DSMB Chairperson will communicate recommendations to the principal investigator in a timely fashion following the close of the DSMB meeting.

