It is important to know that long-term use of CBD has not been studied in any patients with seizures/epilepsy. The risks to younger children, when considering growth and development, from long-term CBD exposure are unknown at this time. Also, there is no specific information available about use of CBD in patients with kidney or liver problems/failure. The study includes frequent visits and safety lab assessments to monitor renal and liver function while participants are taking CBD.

GW Pharma will not participate in the analysis of our study data. GW will collect certain data from our study to perform their own analysis.

Members of the DSMB will include:

[name], PhD (Chair of the DSMB)
[name]
[name].
[name].
[name], Statistician

The DSMB members will not perform any protocol driven activities or procedures.

Data Analysis

The Adult and Pediatric protocols will enroll a combined total of 100 subjects. The data analysis will be split into groups based on age ranges. The groups will be divided as follows: Toddler/Early Childhood (1-5 years of age), Middle Childhood (6-11 years of age), and Early Adolescence (12-18 years of age), and Adults (19+ years of age).

After the 100 subjects have been enrolled and followed for 1 year the following data analysis will be performed:

1. The safety outcome measures will be the Primary Measure and will include:
 - a. Severe adverse events (increase in seizure frequency by more than 100% leading to emergency room visit or hospitalization),
 - b. Change in resting blood pressure or heart rate by 25% if considered significant by managing neurologist,
 - c. Any change in, CBC, CMP, Liver function tests (LFTs), Urinary Analysis or Antiepileptic drug (AED) levels considered by managing neurologists as clinically significant. Clinically significant will be determined by using the Common Toxicity Criteria for Adverse Events (CTCAE) Version 4.03. Adverse events categorized as a grade 3 or above will be considered clinically significant. Adverse Events graded 4 or above will be considered severe adverse events (SAE).

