The analysis plan is focused on safety. The information on safety will be tabulated as the percent of participants with each safety outcome AE and SAE, or others reported as meaningful as well as the number of occurrences of each AE and SAE. This enables an event rate calculation per exposure time as well as the average number of occurrences per participant with an AE or SAE. In addition, common AEs and SES ($\geq 10\%$) will be assessed estimating the time to the occurrence of such endpoints to provide clinically meaningful data on what can be expected when in the course of therapy. This will be summarized using Kaplan-Meier survival curve approaches.

When the sample size is 100 (50 patients from the adult protocol and 50 patients from the pediatric protocol), a two-sided 90% confidence interval for a single proportion using the large sample normal approximation will extend 0.049 from the observed proportion for an expected proportion of 0.10; 0.066 when the event rate is 0.20; 0.075 when the event rate is 0.30; 0.081 when the event rate is 0.40 and 0.082 when the event rate is 0.50.

2. The secondary analysis will assess the frequency and severity of seizures outcome measures will include:
 - a. Decrease in seizure frequency as measured in total number of seizures per month,
 - b. Decrease in seizure severity as measured by the Chalfont Seizure Severity Scale (Duncan & Sander, 1991, JNNP).

The analysis plan for frequency and severity of seizures (secondary outcome) will assess the pattern of change over time. Since the baseline measure is reported at the time of screening there may be some tendency to overestimate the severity in the historically reported interval. This can be examined by comparing the initial study visits improvement versus the pattern of control over time. This will be assessed using

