## Statistical Analysis Plan

The UAB Pediatric CBD Program enrolled 89 treatment resistant epileptic children ages 1-19 years old. All study participants received Epidiolex drug (Cannabidiol; CBD) as an add-on to their previously stable anticonvulsive treatment after baseline assessment. Participants received a starting dose of CBD at 5 mg/kg/day in twice daily dosing and titrated by 5 mg/kg/2 weeks up to 25 mg/kg/day, with a maximum dose of 50 mg/kg/day. Seizure frequency, severity, and adverse events together, with other clinical participant measures, were assessed at baseline and bi-weekly for the duration of the study.

The first 12-months (1-year) of follow-up data were analyzed as follows:

1. The primary outcome measures included:

- a. Severe adverse events (increase in seizure frequency by more than 100% leading to emergency room visit or hospitalization),
- b. Change in resting blood pressure or heart rate by 25% if considered significant by managing neurologist,
- c. Any change in, CBC, CMP, Liver function tests (LFTs), Urinary Analysis or Antiepileptic drug (AED) levels considered by managing neurologists as clinically significant. Clinically significant will be determined by using the Common Toxicity Criteria for Adverse Events (CTCAE) Version 4.03. Adverse events (AE) categorized as a grade 3 or above will be considered clinically significant. Adverse Events graded 4 or above will be considered severe adverse events (SAE).

The analysis plan was focused on safety. The information on safety was tabulated as the percent of participants with each safety outcome AE and SAE, or others reported as meaningful as well as the number of occurrences of each AE and SAE. This enabled an event rate calculation per exposure time as well as the average number of occurrences per participant with an AE or SAE.

2. The secondary analysis assessed the frequency and severity of seizure outcome measures to include:

- a. Mean (SD) and median (IQR) decrease in seizure frequency as measured in total number of seizures per month.
- b. Mean (SD) and median (IQR) decrease in seizure severity as measured by the Chalfont Seizure Severity Scale (Duncan & Sander, 1991, JNNP).

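### The primary SAE tabulation has no single meaning: item 1c labels CTCAE grade 4 or above events as SAEs, against the protocol's own outcome-based definition

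*Protocol*

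**What the plan says.** **Definition by outcome.** The protocol's Serious Adverse Events section states: "Any AE that results in any of the following outcomes will be considered an SAE". The list follows 21 CFR 312.32: death, threat to life, admission, disability, birth defect and important medical events. Convulsions that do not lead to admission are among its examples of the last. The section then separates the two ideas: "Seriousness (not severity) serves as a guide for defining regulatory reporting obligations".

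**Definition by grade.** Item 1c of the protocol's Data Analysis section, repeated in the SAP's primary outcomes, states: "Adverse Events graded 4 or above will be considered severe adverse events (SAE"). The item concerns changes in blood counts, chemistry, liver tests, urinalysis and AED levels. It sets grade 3 as the threshold for clinical significance.

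**A third use.** Item 1a (Specific Aims, Data Analysis and SAP) uses *severe adverse events* for a more than doubled seizure frequency that ends in an emergency room visit or admission.

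**Where the label is used.** The protocol's tabulation sentence reads "The information on safety will be tabulated as the percent of participants with each safety outcome AE and SAE", and the SAP's reads "The information on safety was tabulated as the percent of participants with each safety outcome AE and SAE". Neither says which meaning applies. The DSMB section's termination rule begins "If more than 25% of participating subjects have severe adverse events (SAEs), deemed to be drug related, indicating an unfavorable benefit-to-risk profile". The second dose-limiting criterion in Dosing Adjustment/Schedule also attaches SAE to the word *severe*. On the denominator, the SAP states: "The UAB Pediatric CBD Program enrolled 89 treatment resistant epileptic children".

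**The concern.** Safety is the primary measure, and the percentage of participants with an SAE is one of its tabulated results. The same three letters stand for an outcome-based category in one section and a severity grade in another, and the protocol itself says that severity and seriousness are different things. In the SAP text available, item 1c is the only sentence that attaches a definition to the abbreviation SAE; the outcome-based definition is neither repeated nor cited. An analyst working from the SAP could produce a table that counts a different set of events from the one the protocol calls SAEs. A reader of the report could not tell which set was counted.

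**Working it through.** **1. The plan's own precision figure.** The only figures attached to the safety proportions are the 90% interval half-widths for 100 subjects in the Data Analysis section. At an event rate of 0.10: 1.645 × √(0.10 × 0.90 / 100) = 0.0493, which agrees with the stated 0.049. These figures are not in dispute. They give a sense of scale below.

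**2. How a symptom-free laboratory value becomes an AE.** The Adverse Events section admits an abnormal laboratory value as an AE if it is clinically significant, even without symptoms. Item 1c places clinical significance at grade 3. A symptom-free grade 4 value is therefore an AE, and under 1c also an SAE.

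**3. Which events count as SAEs.** Item 1c can be read in three ways, compared here with the Serious Adverse Events section on its own:

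| Event | Serious section alone | 1c for laboratory values only, Serious section for the rest | 1c replaces the Serious section | 1c adds to the Serious section |
|---|---|---|---|---|
| Admission for a non-laboratory event below grade 4 | Yes | Yes | No | Yes |
| Convulsion below grade 4, no admission, judged an important medical event | Yes | Yes | No | Yes |
| Symptom-free grade 4 laboratory value | Only if judged important | Yes | Yes | Yes |
| Grade 4 non-laboratory event with no other listed outcome | Only if judged important | Only if judged important | Yes | Yes |
| Item 1a event with emergency room visit only, below grade 4 | Only if judged important | Only if judged important | No | Only if judged important |

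No two columns agree throughout. The replacing reading both drops and adds events. The other two only add. The last row shows that an event which 1a calls a severe adverse event need not be an SAE under any of the four.

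**4. Is it only a slip of wording?** In part. The five phone-visit lists say *severe* and eight in-person visit lists say *serious*, all with the same seizure example, so the two words are often swapped. That does not explain 1c. Replacing *severe* with *serious* there would still define an SAE by a grade threshold.

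**5. Size per participant.** With all 89 enrolled as denominator:
- 1 participant: 1/89 = 1.1 points
- 3 participants: 3/89 = 3.4 points
- 5 participants: 5/89 = 5.6 points
- 9 participants: 9/89 = 10.1 points

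The counts 3, 5 and 9 are illustrations, not estimates. Five reclassified participants would move the figure by about as much as the stated half-width of 4.9 points at a 10% rate.

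**6. Where the 25% line falls.**
- At 12 subjects: 3/12 = 25.0% does not exceed it; 4/12 = 33.3% does.
- At 89 subjects: 22/89 = 24.7% does not; 23/89 = 25.8% does.

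A single reclassified participant matters to the rule only if the drug-related count already stands at that line.

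**The case against.** The strongest reply is that the grade sentence closes a laboratory item and may govern laboratory changes only. If so, the overlap with the outcome-based definition is small and admissions below grade 4 stay in the count. That is a fair reading. But the sentence speaks of adverse events without restriction, and even the narrow reading adds laboratory values that the Serious Adverse Events section would count only on medical judgement.

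A second reply is that nothing is lost. Events not counted as SAEs still appear in the AE figures, the 1a outcome can be counted as spelled out, and severity and seriousness are both recorded, so either table can be made. This stands. It limits the harm to the meaning of one reported percentage.

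A reader might infer that the ambiguity could decide whether the trial stops under the 25% rule. The documents do not support that. The rule sits among sentences that use SAE for expedited reporting, directly after the outcome-based definition, and the withdrawal list says *serious*. Dose-limiting criterion 1 already covers every CBD-related event of grade 3 or above, so a grade-4-only criterion 2 would add only events not attributed to CBD. Context therefore favours the outcome-based definition in both places. The DSMB also reviews all data, receives every documented SAE whatever its cause, and may recommend stopping on the totality of evidence. No SAE rate is given under any reading. The nearest figures are 2/151 (1.3%) discontinuing for adverse events and related convulsion in 11/213 (5%). Neither is an SAE rate, and neither points to one near 25%. Probabilities of crossing the line would rest on invented rates.

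**Conclusion.** The concern holds for the SAE tabulation. Item 1c contradicts the protocol's own definition, and 1a adds another meaning to the same wording. This is a conflict between stated rules in a primary safety result, not a missing detail, and it should be corrected.

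That the inconsistency exists is certain; its numerical effect is unknown. It is 1.1 points per reclassified participant, assuming the denominator is the 89 enrolled, and the documents do not say how many participants would be reclassified. The direction depends on the reading: the count can only rise if 1c is laboratory-only or additive, and can move either way if 1c replaces the outcome-based definition. For the 25% rule and the dose-limiting criterion the fault is secondary, a matter of wording, and no effect on stopping is shown.

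**What to change.** - Reserve SAE for the definition in the Serious Adverse Events section, and copy that definition into the SAP.
- In item 1c of both documents, call the events CTCAE grade 4 or above, without the abbreviation SAE.
- In item 1a, wherever it appears, name the seizure outcome directly.
- Tabulate serious AEs and grade 4 or above AEs in separate rows.
- As a secondary wording correction, write *serious* for *severe* in the 25% rule and in dose-limiting criterion 2.

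The reporting sentence "Any severe and unexpected SAE's will be reported to the Food and Drug Administration agency" should be left alone. Substituting *serious* there would merely repeat what SAE already says. If *severe* was meant to limit by intensity, it would also widen what is reported.

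No new data are needed, because the Adverse Events section already requires severity, relationship to CBD and seriousness for each AE. Since the SAP is written in the past tense, the practical cost is to re-tabulate and relabel the safety table. The reported SAE percentage may change, and earlier DSMB counts may need a note stating which definition they used.
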